3.3.4.2 Discontinuation of the trial by the sponsor

AbbVie/ Boehringer Ingelheim reserves the right to discontinue the trial overall or at a particular trial site at any time for the following reasons:

- a. Emergence of any efficacy/safety information that could significantly affect continuation of the trial or any other administrative reasons.
- b. Violation of GCP, the clinical trial protocol (CTP), or the contract by a trial site or investigator, disturbing the appropriate conduct of the trial.

The investigator / the trial site will be reimbursed for reasonable expenses incurred in case of trial termination according to option a.

Proprietary confidential information.

© 2018 Boehringer Ingelheim International GmbH or one or more of its affiliated companies. All rights reserved.

This document may not - in full or in part - be passed on, reproduced, published or otherwise used without prior written permission.

4. TREATMENTS

4.1 TREATMENTS TO BE ADMINISTERED

BI 655066 is supplied by Boehringer Ingelheim, and will be administered subcutaneously.

4.1.1 Identity of BI 655066 and comparator product(s)

The characteristics of the test product for s.c. administration are below.

Substance:	BI 655066: Anti-human IL23p19 mAb
Pharmaceutical formulation:	
Chemical name:	Anti-human IL-23p19 mAb
Molecular weight:	Approximately 148 kDa
Source:	Boehringer Ingelheim Pharma GmbH & Co. KG
Unit strength:	90 mg BI 655066 in a pre-filled syringe with 1 ml (concentration 90 mg/ml)
Posology	Multiple doses
Route of administration:	s.c.

4.1.2 Method of assigning patients to treatment groups

Patients will receive a single dose of open label BI 655066 every 12 weeks. The initial dose for all patients moving into the open label extension study will be 90 mg.

If response is maintained, i.e. achievement of PASI₉₀ at Extended visit 2, 90 mg dosing will occur every 12 weeks until Extended EOT.

If there is a lack of response, defined as response below PASI₉₀ at Extended visit 2, the dose should be increased to 180 mg, and the 180 mg dosing will occur every 12 weeks until Extended EOT.

Detailed instructions for preparation of BI 655066 for administration of each dose will be given in the ISF.

4.1.3 Selection of doses in the trial

The treatment is derived from the treatment groups in the preceding phase II trial, where the dose selection is based on the completed phase I trial in which clinical improvement in patients with psoriasis was observed across a wide dose range (~18 mg -375 mg).

The choice of the “90 mg/dose” was based on several pieces of data obtained in the initial 1311.1 single-dose, dose-escalation study: an analysis of dose given (and the subsequent “area under the curve” exposure data) plotted against the clinical response based on the PASI

Proprietary confidential information.

© 2018 Boehringer Ingelheim International GmbH or one or more of its affiliated companies. All rights reserved.

This document may not - in full or in part - be passed on, reproduced, published or otherwise used without prior written permission.

score noted that the stable effective dose was likely to be greater than 1.0 mg/kg (approximately 90 mg)

Subsequent to selection of the starting dose for 1311.13, an interim analysis of 1311.2 indicated that the 180 mg dose resulted in a numerically higher proportion of patients who achieved PASI90. Since the higher dose was not associated with a higher incidence of any specific adverse events, patients who do not achieve PASI90 on the 90 mg dose are eligible to receive the higher dose of 180 mg. This dose is also consistent with the objective of obtaining safety data on a dose equal to or greater than the proposed “to be marketed” dose of 150 mg, allowing us to obtain additional safety information appropriate for inclusion in future discussion with health authorities.

4.1.4 Drug assignment and administration of doses for each patient

The study drug will be administered by the physician investigator or by authorised study personnel (e.g. study nurse). The study drug will be administered as a subcutaneous injection in the abdomen, thighs, gluteal regions, or upper arms. Injections being given in the same area should be at least 2 cm apart and should not be close to a vein. The injection site should avoid sites of psoriasis involvement as well as sites where the skin is tender, bruised, erythematous, or indurated, and should be alternated to other areas for subsequent doses.

Further information regarding technique of injection and injection materials (syringes, needles) will be provided in the ISF. For 180 mg doses, two syringes of 1 ml BI 655066, each of 90 mg, will be allocated and injected. Dilution of the study medication is not allowed and no dose modification, apart from the protocol specified doses, is permitted.

Administration of biologic agents involves the risk of local (injection site) or systemic hypersensitivity reactions. Therefore the patients should be closely monitored for signs and symptoms of hypersensitivity reactions for approximately 1 hour after the first dose administered, and 30 minutes following all other doses of study drug. Study personnel should observe the injection site for signs of redness, swelling or hardness. They should also ask subjects about itching, dizziness or shortness of breath. Patients should be advised that if they experience redness, swelling or other changes at the injection site, they should notify site personnel. They should further be advised that if they experience itching all over or a feeling of being swollen, dizzy or short of breath, they should notify site personnel or their own healthcare provider immediately.

Vital signs will be taken pre-dose, 5 minutes, and 1 hour (at roll-over visit) or 30 minutes (at following visits) after the dose is administered (cf. [Flow Chart](#)). Hypersensitivity reactions should be treated according to medical standards. Pre-medications for further injections might be considered and will be agreed on between investigator and BI clinical monitor.

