7. "xT" is a targeted physical examination including assessment of vital sign measurements, and evaluation of organ systems associated with AE(s) symptoms or laboratory abnormalities.
8. Measured after 5 minutes of rest in the supine position. Measurements of vital signs should, if possible, always precede blood sampling.
 - a. Extended visit 1: Vital signs will be taken ~ 30 min pre-dose, 5 minutes, and 1 hour after the dose is administered
 - b. Following dosing visits: Vital signs will be taken ~ 30 min pre-dose, 5 minutes, and 1 hour after the dose is administered
 - c. Non-dosing visit (Extended EOS): Vital signs will be measured once per visit
9. ECG to be performed after 5 minutes of rest in the supine position, at every 24 weeks, starting from EV1 (EV1, EV3, EV5...). Should, if possible, be performed prior to blood sampling.
10. Not to be performed for patients who prematurely discontinue the treatment period.
11. All new AEs as well as unresolved AE from the preceding trial 1311.2 should be followed up within this study.
12. Only for patients with psoriatic arthritis.
13. For details of laboratory tests cf. [Section 5.2.3](#), [Table 5.2.3:1](#) and [5.2.3.2](#)
14. Patients must be fasting for at least 8 hours prior to collection of the safety laboratory samples.
15. Only applicable for women of childbearing potential.
16. In women of childbearing potential urine pregnancy test has to be performed before each administration of study drug.
17. Blood samples for protein biomarker, PK and ADA will be drawn ~ 30 min before the subcutaneous injection (PreD) at every 24 weeks, starting from EV1 (EV1, EV3, EV5...).
18. For patients who prematurely discontinue the follow up period before study end (for any reason), an early Extended EOS visit is required. This early Extended EOS visit will include the same procedures as the normal Extended EOS visit.
19. Patients will be asked to give consent to be contacted (or for their primary care physician to be contacted) by the study team to obtain vital status information preferably at the time of study entry
20. Only required at EV1 for patients who are having EV1 as their first 1311.13 visit
21. All efficacy assessments should be performed pre-dose (PreD)
22. To be repeated once per year until study end (EV1, EV5, EV10...)

Proprietary confidential information.

© 2018 Boehringer Ingelheim International GmbH or one or more of its affiliated companies. All rights reserved.

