Major adverse cardiovascular events (MACE), including myocardial infarction, cerebrovascular accident, and cardiovascular death, have been initially reported in association with the anti-IL-12/23 agents, ustekinumab and briakinumab, in patients with psoriasis. However, such a risk has not been confirmed among patients receiving ustekinumab for up to five years ([R13-3518](#)). The overall risk of MACE in the present study is considered to be low.

Local reactions to i.v. and s.c. administered biologic agents are uncommon, and are usually limited to redness, swelling or induration at the injection site. Manifestations of systemic hypersensitivity reactions include anaphylaxis, pruritus, hypotension, and respiratory distress. Both local and systemic hypersensitivity reactions are readily detectable, transient in nature, and manageable with standard medical treatment. No systemic hypersensitivity reactions have been reported with BI 655066 to date. Patients will be closely monitored 30 minutes to 1 hour after drug administration for signs of redness, swelling or hardness at the injection site or generalized itching, dizziness or difficulty breathing.

Although rare, a potential for drug-induced liver injury is under constant surveillance by sponsors and regulators. Therefore, this study requires timely detection, evaluation, and follow-up of laboratory alterations of selected liver laboratory parameters to ensure patients' safety (cf. [section 10.4](#)).

The study has been designed, and will be conducted in such a manner as to limit these risks as much as possible. In order to mitigate any safety signals as early as possible, an independent Data Monitoring Committee (DMC) will oversee this study. Since all patients will receive active treatment at a dose of, or greater than the projected marketed dose, most patients will likely have a benefit from participating in this study. Therefore, the benefit-risk assessment is considered appropriate for a clinical trial of an experimental therapy at this stage of development.

Proprietary confidential information.

© 2018 Boehringer Ingelheim International GmbH or one or more of its affiliated companies. All rights reserved.

This document may not - in full or in part - be passed on, reproduced, published or otherwise used without prior written permission.

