### **Definition of Analysis Windows**

All time points and corresponding time windows are defined based on Rx Days.

For efficacy analyses, local tolerability, laboratory parameters, study drug injections, and vital sign variables, analysis windows are constructed using the following algorithm:

- Determine the nominal Rx day for each visit (e.g., Week 4 [4 weeks after Baseline visit] equals Rx Day 29).
- In order to include all post baseline data, the first post-baseline interval starts on the first day after the first dose of risakizumab (Rx Day 2).
- Determine the window around a specific nominal Rx day by adding or subtracting half of the interval between adjacent visits (e.g., days between Week 2 and Week 4 is 14). The threshold between adjacent visits is determined by splitting the interval evenly between the visits. If the resulting

split is between Rx days, then the threshold is determined as the midpoint between the adjacent visits. If the resulting split is on an Rx day, then the threshold is determined as being between that Rx day and the Rx day prior to it (e.g., the split between Week 2 and Week 4 would be between Rx Days 22 and 23).

- If more than one assessment is included in a time window the assessment closest to the nominal day will be used. If there are two observations equidistant to the nominal day, the one after the nominal day will be used in analyses. If more than one post baseline assessment is included on the same day, then the worst assessment on that day will be used in analyses, except those specified in Section 11.0.

The protocol specified visits and corresponding time windows used in the efficacy analyses, study drug injections, local tolerability, clinical laboratory tests, and vital sign variables, are presented in the following **Table 1**.

**Table 1. Visit Windows for Analysis of PASI, sPGA, Pain Vas, DLQI, Study Drug Injections, Local Tolerability Assessment, Clinical Laboratory Tests, and Vital Signs**

Window label	Target day	Interval
Entry of this study a	1	$\leq 1^b$
Week 12	85	[2, 127]
Week 24	169	[128, 211]
Week 36	253	[212, 295]
...	...	...
Week K	$K \times 7 + 1$	$[K \times 7 - 40, K \times 7 + 43]$

a. There is no local tolerability measurements at entry of this study (Extended Visit 1).

b. If time is collected in vital signs, restrict to records prior to the first dose of RZB.

Note: Rx Day calculated relative to first dose date of risakizumab in this study.

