**11.4.2 Statistical Methods**

Observed values at each scheduled visit in vital sign parameters will be summarized with the mean, standard deviation, median, minimum and maximum. If there are multiple post-baseline measurements on the same day, average value will be used.

For systolic blood pressure, diastolic blood pressure and pulse, a listing of all subjects with any vital sign value meeting criteria for potentially clinically important values will be provided. For each of these subjects, the whole course of the respective parameter will be listed. The number and percentage of subjects who have at least one value meeting criteria for potentially clinically important values will be provided for each vital sign parameter.

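### After the first dosing visit, the Flow Chart puts the last post-dose vital-sign reading at 1 hour and Protocol 4.1.4 puts it at 30 minutes; the two must be reconciled

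*Protocol*

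**What the plan says.** Flow Chart footnote 8 sets the vital-sign times. For the first extended visit, 8a reads: "Extended visit 1: Vital signs will be taken ~ 30 min pre-dose, 5 minutes, and 1 hour after the dose is administered". For the later dosing visits, 8b repeats the same three times: "Following dosing visits: Vital signs will be taken ~ 30 min pre-dose, 5 minutes, and 1 hour after the dose is administered". Visits without dosing have a single reading (8c).

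Protocol 4.1.4 describes the same measurements as pre-dose, 5 minutes, and then "1 hour (at roll-over visit) or 30 minutes (at following visits) after the dose is administered", with a cross-reference to the Flow Chart. A separate sentence in that section sets the observation period for hypersensitivity reactions: "approximately 1 hour after the first dose administered, and 30 minutes following all other doses of study drug". Protocol 2.3 gives only a range that is not divided by visit: "Patients will be closely monitored 30 minutes to 1 hour after drug administration".

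On the analysis side, SAP 11.4.2 summarises vital signs by visit and states: "If there are multiple post-baseline measurements on the same day, average value will be used". For the screen of potentially clinically important findings it plans "a listing of all subjects with any vital sign value meeting criteria for potentially clinically important values will be provided". SAP section 6.0 limits the risankizumab baseline to values before the first dose, and note b to SAP Table 1 adds for the study-entry window: "If time is collected in vital signs, restrict to records prior to the first dose of RZB". No such limit is attached to later visits.

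**The concern.** Two operative passages give different times for the same scheduled safety measurement, and one of them sends the reader to the other as if they agreed. A site that takes only the scheduled readings cannot satisfy both.

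What is at stake is modest. A deviation could be charged against a site whichever passage it followed. The last post-dose reading could also mean 30 minutes at one site and 60 minutes at another, with nothing in the SAP to tell them apart. Long-term safety is the primary objective (Protocol 2.2), and vital signs are among the listed safety assessments (Protocol 5.2.1.3 and 7.3.3), so the time of measurement should be clear.

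**Working it through.** The plan gives no figure to reproduce. The check is a comparison of passages, a count of visits, and a look at what the SAP does with the readings.

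**1. The times side by side**

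| Visit | Flow Chart footnote 8 | Protocol 4.1.4 | Result |
|---|---|---|---|
| First extended / roll-over visit | pre-dose, 5 min, 1 hour | pre-dose, 5 min, 1 hour | agree |
| Following dosing visits | pre-dose, 5 min, 1 hour | pre-dose, 5 min, 30 min | conflict |

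The gap is 60 − 30 = 30 minutes, for the last reading only. Both passages are current protocol text, not amendment-log text.

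**2. Does another passage settle it?**

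- Protocol 2.3 gives a range that contains both times.
- Protocol 5.2.5 sends the reader to the Flow Chart for vital-sign time points, and Protocol 6.1 does so for procedures in general. Neither says that the Flow Chart prevails over 4.1.4.

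The names of the first visit also differ: 4.1.4 says roll-over visit, footnote 8a says Extended visit 1. The heading of 6.2.2.1 equates them. Protocol 5.2.3, however, uses initial roll-over visit for patients whose Extended visit 1 is their first visit in this trial. For patients carried over from the earlier schedule, Extended visit 1 was not their first visit, so the conflict could reach that visit too.

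**3. How many visits**

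- Nominal, weeks 12 to 192 at 12-week steps: (192 − 12)/12 + 1 = 16.
- Nominal, to week 204: (204 − 12)/12 + 1 = 17. The Flow Chart lists a visit at week 204, but the table as read does not show clearly whether a dose is given there.
- Attainable by calendar: the extended schedule came in with global amendment 3, dated 10 June 2015. After 1 May 2018 and country approval of the current amendment, the next visit is the last one. From 10 June 2015 to 1 May 2018 is 3 × 365 + 1 − 40 = 1,056 days, or 1,056/7 = 150.9 weeks. Since 150.9/12 = 12.6, a patient who started on the first possible day reaches 12 later dosing visits (weeks 12 to 144). A later start lowers this; late approval of the current amendment raises it.

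**4. What the SAP does with the readings**

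Under either passage a later dosing visit yields three sets of readings. The same-day average gives each a weight of 1/3. If a patient's value at 30 minutes differs from that at 60 minutes by d, the visit value moves by d/3. The pre-dose and 5-minute readings, with combined weight 2/3, are pooled whichever time is used. The pooling of pre-dose with post-dose values therefore exists without the conflict; the conflict only makes the third component ambiguous.

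The screen for clinically important findings uses any value and does not average. The number of scheduled readings is the same under both passages, so only the timing of one screened reading changes.

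**The case against.** The best answer is that the protocol directs sites to the Flow Chart (5.2.5 and 6.1), so most would probably follow footnote 8b. The cross-reference in 4.1.4 is a cf., which the abbreviations list defines as compare, so it does not claim to restate the Flow Chart. This makes divergence less certain, but it does not remove the conflict: there is no precedence rule, and a reader of 4.1.4 has an explicit, different time in front of them.

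Three stronger readings are tempting and should be resisted.

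- A reader might infer that sites did measure at different times and that the data are mixed. The documents report no site practice; they show only that this could happen.
- A reader might infer that the length of hypersensitivity observation is itself contradicted. That rule is a separate sentence in 4.1.4, the range in 2.3 is compatible with it, and no other passage states a different period. A site following 8b would need the patient present for the 1-hour reading, but that is an indirect effect.
- A reader might blame the conflict for the SAP's mixed visit values. The averaging rule pools pre-dose and post-dose readings in any case.

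It is also fair to object that analysis by time point presupposes recorded times, and note b to SAP Table 1 leaves that open. This stands, and the SAP part of the fix is conditional for that reason.

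**Conclusion.** The inconsistency is real and limited to one item: the last post-dose vital-sign reading at dosing visits after the first, with a 30-minute difference between footnote 8b and Section 4.1.4. It recurs at each later dosing visit a patient attends: 16 or 17 on the nominal schedule, and about 12 by the calendar under the assumptions shown (start on the date of amendment 3, prompt approval of the current amendment).

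The effect on conclusions is small. The trial has no hypothesis tests, vital signs are a further safety measure and not a primary endpoint, and the affected reading carries one third of the averaged visit value. The point is worth correcting because it bears on what sites are asked to do at each later dose and costs almost nothing to settle.

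**What to change.** - **Protocol:** reconcile footnote 8b and Section 4.1.4 to one stated time for following dosing visits, use one name for the first visit in both places, and inform sites. Which time is right is for the sponsor to decide. The cost is a wording change and a site clarification.
- **SAP 11.4.2:** if assessment times or time-point labels are recorded, replace the same-day average for later visits with separate summaries of the pre-dose, 5-minute and last post-dose readings, classing the last by its recorded time. If times are not recorded, say so and state that the visit value pools pre-dose and post-dose readings. The cost is a short text change and some extra table rows; no new data are needed.

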4.1.5 Blinding and procedures for unblinding

Not applicable.

In this open-label trial, treatment allocation will not be concealed throughout the study. The CRF will contain information on treatment.

Proprietary confidential information.

© 2018 Boehringer Ingelheim International GmbH or one or more of its affiliated companies. All rights reserved.

This document may not - in full or in part - be passed on, reproduced, published or otherwise used without prior written permission.

4.1.6 Packaging, labelling, and re-supply

BI 655066 supplies will be provided by Boehringer Ingelheim (cf. [Section 4.1.1](#) for more details regarding the supplies). Pre-filled syringes of study medication will be provided in individual boxes identified with the trial number, batch and medication number. Supply of study medication will be managed by the IRT.

For details of packaging and the description of the label, refer to the ISF.

4.1.7 Storage conditions

The trial medication must be stored securely, e.g. in a locked refrigerator or at a pharmacy, in their original packaging. It may only be dispensed to trial patients according to the clinical trial protocol, by authorised personnel as documented in “Trial Staff List”.

Drug supplies should be stored as indicated on the country specific booklet page. A temperature log must be maintained. If the storage conditions are found to be outside the specified range, immediately contact the local clinical monitor as provided in the lists of contacts.

Further details are provided in the Investigator’s Brochure and on the country specific labels of which a sample will be maintained in the ISF.

